1.2 Schedule of Assessments

Following screening, informed consent, and confirmation that a patient with severe COVID-19 meets all eligibility criteria, subjects will be randomized 1:1 to receive duvelisib 25 mg, po BID or a placebo pill, po BID. Randomization between duvelisib 25 mg po BID and placebo BID will be stratified by study site. The investigational pharmacy will supply coded study drug based upon the results of central randomization.

Procedures and Tests Study Tests DURING HOSPITALIZATION [#]	Days -2 to 0 [@]	Day 1 [@]	Day 8 (± 2)	Day 15 (± 2)	Day 29 (± 3)	Day 50-60
Randomization to duvelisib or placebo arm	X					
Study Drug Administration		Oral drug BID Days 1-14				
SARS-CoV-2 RT-PCR	X					
Immunophenotyping of immune cells in blood		X	X	X	X	
Whole blood for RNA gene expression ^{##}		X	X	X	X	
Mononuclear cells for mass cytometry ^{##}		X	X	X	X	
Plasma cytokines and chemokines ^{##}		X	X	X	X	
Anti-SARS Cov-2 IgG		X			X	
TSH	X				X	
Hepatitis Serologies if known history of treated Hepatitis B or C	X					

Standard of Care Tests*	Days -2 to 0	Day 1	Day 8 (± 2)	Day 15 (± 2)	Day 29 (± 3)	Day 50-60
Physical Exam	X	Performed daily during hospitalization				
ECOG Performance Status	X	Performed daily during hospitalization				
Vital Signs	X	Performed daily during hospitalization				
Clinical Labs: Record data in eCRF (REDCap) during hospitalization as shown below						
CBC with differential	X	Abstract data as available				
CMP	X	Abstract data as available				
Ferritin		Abstract data as available				
CRP, Troponin		Abstract data as available				
Coagulation Tests**		Abstract data as available				
Non-contrast Chest CT or Chest X-Ray	X	Abstract data as available				
Serum or Urine Pregnancy Test***	X					
Assessment of Survival Status						X

study procedures which are performed as part of the research protocol and covered by the study budget

Additional research blood samples will be obtained prior to discharge from hospital

@ Some overlap of procedures and tests performed for screening and Day 1 is expected.

* Standard of care procedures which are routinely performed on COVID-19 patients and the results of which will be recorded as part of study conduct

** PT/INR, PTT, Fibrinogen, D-Dimer, Heparin/Enoxaparin Anti Xa

*** Pregnancy test for WOCBP may be obtained after hospital admission but prior to study enrollment

2. Objectives (and Endpoints)

OBJECTIVES	ENDPOINTS
Primary	

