3.6 PI3K inhibitors in clinical settings

PI3-kinase (PI3K) inhibitors are FDA-approved for treatment of relapsed follicular lymphoma (FL) and CLL/small lymphocytic lymphoma (SLL). Orally bioavailable drugs are typically dosed once or twice a day with the goal of inhibiting signaling through the PI3K-AKT pathway causing reduction in the growth of malignant lymphoma cells and induction of apoptosis. PI3K inhibitors are generally well tolerated and can be given for weeks to months as continuous therapy without significant hematological toxicity. One common feature of treatment with PI3K inhibitors is the development of late autoimmune disease, typically after more than 1 month of drug exposure, including colitis, pneumonitis and rash, that appears to be a consequence of blocking differentiation and down-regulation of regulatory T cells (12, 27).

4. Study Intervention/Investigational Agent

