- EKG as ordered by attending physician
- Labs: Complete Blood Count (includes hemoglobin, platelets, and white blood cell count with differential), Comprehensive metabolic panel (includes sodium, potassium, chloride, creatinine, AST, ALT, total bilirubin, and alkaline phosphatase), ferritin, D-dimer, CRP, troponin (abstract from SOC labs daily or as available), Thyroid Stimulating Hormone (TSH, Day 29)
- Immune phenotyping of leukocytes (days 1, 8, 15, and 29)
- Whole blood for RNA – gene expression analyses (days 1, 8, 15, and 29)
- Mononuclear cells for mass cytometry (CyTOF) (days 1, 8, 15, and 29)
- Plasma for cytokine/chemokine analyses (days 1, 8, 15, and 29)
- Serum for antibodies to SARS-CoV-2 (screening and 29)

Follow-up Phase:

- Survival status on day 50 - 60

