8.1 Duration of therapy and follow up

In the absence of treatment delays due to adverse event(s), subjects will be treated for 14 days with duvelisib/placebo. A subject will be considered to have completed the study if he or she has completed all phases of the study including the last visit or the last scheduled procedure shown in the schedule of activities. Subjects who have signed consent, are deemed eligible and are randomized to receive study drug (duvelisib/placebo) will be considered evaluable for efficacy endpoints on an intent-to-treat basis. Subjects who receive at least one dose of study drug (duvelisib/placebo) will be evaluable for toxicity. The end of the study is defined as completion of the last visit or procedure in SOA (Day 29) and an assessment of survival status on day 50 - 60. In the event of a subject's withdrawal, the Investigator will make every effort to complete the End of Treatment procedures specified in the Schedule of Events. Subjects who withdraw from the study will be encouraged to permit follow-up for clinical end-points, including death, mechanical ventilation (e.g. intubation, high-flow O₂ Bi-PAP or AIRVO), hospital discharge, and need for supplemental oxygenation. Subjects will be assessed daily while hospitalized. If the subjects are discharged from the hospital, they will have phone follow-up calls with a study team member at

Protocol Title: Duvelisib Ameliorates Manifestations of Pneumonia in Established Novel Coronavirus Infection (DAMPEN-CI)

day 15 (window d13 – 25), and at day 29 (window d27 - 39) for clinical outcomes data. Arrangements will be made for an outpatient phlebotomy appointment after day 29 (day 30 - day 60 if possible, but up to day 100) to obtain safety laboratory tests and blood samples for secondary research. Patients will receive \$100 compensation for the in-person follow-up phlebotomy visit. However, travel distance, infection control or other restrictions may limit the ability of the subject to return to the clinic. In such cases, only clinical data will be obtained via the d27 - 39 call.

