Immune related toxicities are the most common non-hematological adverse event (AE) with duvelisib. Elevated AST/ALT and diarrhea are the most common non-hematological AEs. The rates of diarrhea ranged from 42-51% in clinical trials with a median onset of 2.2-4 months (28, 8). The median time of onset for AST/ALT elevation was 1.2 months and occurred in 39% of patients in one phase I clinical trial (28). Other non-hematological AE's that have been reported include:

- 1) risk of infection (reported in 61-69% of patients with upper respiratory tract infections and pneumonia being the most common infections (8, 29).) There have also been reports of *Pneumocystis jirovecii* with the use of duvelisib.
- 2) risk of pneumonitis,
- 3) risk of intestinal infection and colitis,
- 4) risk of severe skin reactions (maculopapular rash)
- 5) Neutropenia (the most common hematological AE, occurring in 29%-39% of patients in clinical trials)
- 6) pyrexia

Other Risks:

Risk of Phlebotomy- The primary risks of phlebotomy include local discomfort, occasional bleeding or bruising of the skin at the site of needle puncture, and rarely hematoma, infection, or fainting. At the time of enrollment and during study visits, each participant will be asked about participation in other research studies to ensure that blood draws do not exceed the following amounts for all research protocols combined: 10.5 mL/kg or 550 mL, whichever is smaller, over any 8-week period for adults, and no more than 5 mL/kg may in a single day (no more than 9.5 mL/kg may be drawn over any 8-week period) for persons under the age of 18.

Risk of Nasopharyngeal Swab- The primary risk of a nasal swab is local discomfort. Rarely, there can be local bleeding from the nasal mucosa, which is controlled with local measures such as pressure or packing with gauze.

Risk of Oropharyngeal Swab- The primary risk of an oropharyngeal swab is local discomfort. This swab can stimulate the gag reflex, and very rarely vomiting.

Risk of Endotracheal Aspirate- The primary risk of endotracheal aspirate is cough, and rarely can cause a small amount of bleeding.

Data security- Subjects will be asked to provide personal health information (PHI). All attempts will be made to keep this PHI confidential within the limits of the law. However, there is a chance that unauthorized persons will

Protocol Title: Duvelisib Ameliorates Manifestations of Pneumonia in Established Novel Coronavirus Infection (DAMPEN-CI)

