At the interim analysis (20 patients/arm), the incidence of death or mechanical ventilation, grade ≥ 3 elevations in liver transaminases, or neutropenia will be estimated. We assume that the underline rate is 40%, 10%, or 24% for the three incidences in placebo group respectively, and if the rate in duvelisib group is $\geq 15\%$ higher than that in the placebo group in either of the three incidences, the trial may be stopped due to the safety concern. It also translates to stop the study if 3 or more excess events in duvelisib group are observed in either of the three incidences. Operating Characteristics, the probability of trial stopping due to ≥ 3 excess events based one simulation study, is listed in the below table.

AEs	Underline event rate in Placebo arm	Underline event rate in Duvelisib arm						
		5%	10%	20%	30%	40%	50%	60%
death or mechanical ventilation	40%	0%	0.02%	0.7%	4.8%	16.6%	37.4%	62.7%
grade ≥ 3 elevations in liver transaminases	10%	0.79%	5.7%	32.8%	65.8%	87.9%	97.2%	99.7%
neutropenia	24%	0.07%	0.6%	7.3%	26.1%	52.7%	77.3%	92.6%

In addition to the study stopping rules based an interim analysis, the Independent Data Monitoring Committee (IDMC) will review, on a monthly basis, the number of Grade 3 and/or Grade 4 adverse events in each arm, including neutropenia and elevated transaminases, and consider stopping or suspending accrual to the study if the frequencies of Grade 3 or Grade 4 adverse events are significantly higher among subjects in the duvelisib arm compared with subjects in the control arm.

Analysis of Safety Data

The primary safety endpoints include death or mechanical ventilation, grade ≥ 3 elvation in liver transminases, and neutropenia within 4 weeks. The cumulative incidence rate of each safety endpoint will be calculated with 95% confidence interval by randomized arms, and compared by Fisher's exact test.

Handing of Missing Data

For the safety endpoints and secondary endpoints, missing data will not be imputed, summaries and analyses will be based on the observed cases. For the primary efficacy analysis, every effort will be made from the informed consent form design to clinical follow up to reduce the missing data. Patients withdraw consent before the primary endpoint can be measured will be replaced.

Demographics and Baseline Characteristics

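### Late toxicity is not secured in any pre-specified between-arm comparison, and the protocol contradicts itself on when adverse-event recording ends

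*Combined protocol and SAP*

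**What the plan says.** **Day 50-60.** The schedule (section 1.2) marks a single row there, "Assessment of Survival Status". The follow-up phase in section 5.5 agrees: "Survival status on day 50 - 60". Section 8.1 lets this be settled from the medical record, by phone or text, through an associate, or by a vital records search.

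**Primary safety endpoints.** Section 15.1 (Analysis of Safety Data) names death or mechanical ventilation, grade 3 or higher transaminase elevation, "and neutropenia within 4 weeks". Arms are compared by Fisher's exact test. Missing safety data are not imputed.

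**Late blood draw.** Section 8.1 arranges an outpatient appointment after Day 29, at Day 30-60 if possible and up to Day 100, "to obtain safety laboratory tests and blood samples for secondary research". If the patient cannot return, only the Day 27-39 phone call remains.

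**End of adverse-event recording.** Section 16.2 (Definition of Adverse Events) runs to withdrawal or completion of the trial. Section 16.1 gives no end date. Section 16.2 (Documenting Adverse Events) stops 14 days after study drug ceases. The secondary endpoint of grade III-V events or SAEs (section 2) carries no time limit.

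**Cited onset.** Section 13: "The median time of onset for AST/ALT elevation was 1.2 months and occurred in 39% of patients in one phase I clinical trial", and "The rates of diarrhea ranged from 42-51% in clinical trials with a median onset of 2.2-4 months". Section 3.6 places late autoimmune toxicity "typically after more than 1 month of drug exposure". Study drug here lasts at most 14 days and stops at discharge if that is earlier (section 4.2.5).

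**The concern.** Section 1.1 makes it a study question whether the two-week exposure is safe and well tolerated. The formal safety comparison closes at 4 weeks, earlier than the median onset the protocol itself cites for liver toxicity. The contact after that asks only whether the patient is alive, and the one planned late laboratory measurement feeds no named analysis. If 14 days of drug did carry delayed toxicity, the randomized comparison that could show it might never be made, although the blood may already have been drawn and the patient already contacted.

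The conflict over when recording ends has a nearer consequence. If the shorter window governs, a patient discharged early leaves adverse-event recording before the 4-week safety endpoints are complete.

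**Working it through.** **1. When does recording stop?** Under Documenting Adverse Events, the window ends on the day of last dose plus 14. The primary safety window is 4 weeks, which section 15.1 equates with 29 days for the primary efficacy endpoint; both Day 28 and Day 29 are shown.

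| Last dose | Recording ends | Short of Day 28 | Short of Day 29 |
|---|---|---|---|
| Day 14 (full course) | 14 + 14 = Day 28 | 0 days | 1 day |
| Day 7 (discharge) | 7 + 14 = Day 21 | 7 days | 8 days |
| Day 5 (discharge) | 5 + 14 = Day 19 | 9 days | 10 days |

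Under Definition of Adverse Events, recording runs to trial completion. Section 8.1 puts that at the Day 29 procedures plus the Day 50-60 survival check. The two rules cannot both apply. With observed-case analysis, the plan does not say whether a patient whose recording closed on Day 19 counts as event-free at 4 weeks or as missing.

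**2. Where would a grade 3 ALT found at the late draw be counted?**
- Primary safety endpoints: not counted, because it falls after 4 weeks.
- Grade III-V/SAE secondary endpoint (compared by arm with Fisher's exact test) and the maximum-grade tables of section 16.1: counted if recording runs to completion, not counted if it stops 14 days after the last dose.
- Late SAE route in section 16.2: only if the event is serious and the investigator suspects causality. That serves regulatory reporting and gives no count by arm.
- An analysis naming the draw: none in section 15.1.

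A symptomatic event first appearing after the Day 27-39 call has even less chance of capture. Section 16.1 collects events by inquiry at study visits. The only in-person contact left is the conditional phlebotomy appointment, and the Day 50-60 check can be completed without speaking to the patient.

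**3. How do the cited onset times sit against the windows?** The medians come from cited studies and can only be converted here. AST/ALT: 1.2 x 30.44 = 36.5 days (33.6 with 28-day months), so 36.5 - 29 = 7.5 days after Day 29. Diarrhea: 2.2 x 30.44 = 67 days to 4 x 30.44 = 122 days.

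The documents give no onset distribution, so shapes are assumed. The share of onsets by day d, for median m, is:
- exponential: 1 - 2^(-d/m)
- log-normal: Phi(ln(d/m)/s), with s from 0.5 to 1.0
- Weibull: 1 - 2^(-(d/m)^k), with k of 1.5 or 2 (AST/ALT only)

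For AST/ALT at Day 29, the exponential gives 1 - 2^(-29/36.5) = 42% and the log-normal with s = 0.5 gives Phi(-0.46) = 32%; the other shapes fall between.

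| Share of onsets by | AST/ALT, m = 36.5 days | Diarrhea, m = 67 days |
|---|---|---|
| Day 29 | 32-42% | 5-26% |
| Day 60 | 68-85% | 41-46% |
| Day 100 | 84-99% | not computed |

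If the contact falls on Day 50, the exponential and log-normal forms give about 61-74% for AST/ALT. All these shares describe the cited dosing. They do not estimate events missed in this trial.

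**The case against.** A reader might infer that late drug toxicity goes uncounted and that the 4-week window biases the trial towards a finding of safety. The documents do not support that.

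- **Recording may extend past 4 weeks.** Section 16.1 and one paragraph of section 16.2 set no 14-day cut-off, and the grade III-V/SAE endpoint is untimed and compared by arm. The reportable list in section 16.2 already includes ALT, AST, bilirubin, diarrhea and repeat hospitalization. If the longer rule governs, late events can be counted. This stands, and it turns the complaint from omission into contradiction.
- **Onset times do not transfer directly.** Section 3.6 ties colitis, pneumonitis and rash to more than a month of drug. Section 3.1 says short exposure may act differently from long exposure, and section 5.1 limits the course to reduce the risk of opportunistic infections. Section 13 does not say that the 1.2-month figure concerns grade 3 or higher elevations, which is the endpoint here. Four weeks covers the whole course plus about two weeks off drug, a defensible choice for primary endpoints. This also stands: whether a course of up to 14 days carries delayed toxicity is unknown, so no bias is shown.
- **A phone or text check cannot find asymptomatic transaminase elevation.** Correct. Liver data must come from the late blood draw.
- **The adverse-event list was narrowed on purpose, for feasibility.** True, and a reason to keep any added questions few.

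None of this places the late draw in the schedule or in an analysis, or settles which recording rule applies.

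**Conclusion.** The point holds in a limited form. No pre-specified between-arm comparison is certain to include toxicity after 4 weeks. The primary safety endpoints exclude it, the Day 50-60 contact asks only about survival, the planned late draw is unscheduled and unanalysed, and the one untimed endpoint depends on which of two conflicting recording rules applies. Under the shorter rule, recording ends on Day 28 at the latest and 7 to 10 days before the 4-week window closes for a patient whose last dose is on Day 5 to 7. Those discharge days are examples; the documents give no distribution of discharge times.

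The onset percentages rest on one cited median per toxicity, assumed shapes and a dosing pattern this trial does not use. They justify looking and do not measure a loss. This is a cheap improvement worth making, not a flaw in the primary safety comparison as defined.

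**What to change.** 1. Reconcile section 16.1 and the two paragraphs of section 16.2. Adverse-event recording should cover at least the full 4-week safety window for every patient, whatever the date of the last dose, and run to the last contact.
2. List the section 8.1 safety draw in the schedule of assessments. Add to section 15.1 a descriptive table by arm, Day 30 to last contact, of grade 3 or higher laboratory results from that draw, with the number of patients sampled per arm.
3. At the existing Day 50-60 contact, also record re-hospitalization and grade 3 or higher events since Day 29, and say whether the question is confined to the reportable list in section 16.2.

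The cost is a few case report form items, one table and a wording change, with no new visit or test. Data will be incomplete for patients who do not return or who are traced only through associates or vital records, so the table should be labelled descriptive, without a formal test.

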To compare the incidence of mechanical ventilation or death in subjects with severe COVID-19 given placebo or oral duvelisib.	The primary end-point is a composite endpoint of mechanical ventilation or death within 4 weeks of randomization.
Secondary	
Secondary Objectives are to compare the duvelisib cohort to the placebo cohort with respect to:
 
1) Days to recovery as assessed by ACTT endpoints as the time to recovery (Day 1 through Day 29) to satisfy a score of ≥ 5 from the following eight categories from the NIAID ordinal scale. The scale is as follows: 1. Death; 2. Hospitalized, on invasive mechanical ventilation or extracorporeal membrane oxygenation (ECMO); 3. Hospitalized, on non-invasive ventilation or high flow oxygen devices; 4. Hospitalized, requiring supplemental oxygen; 5. Hospitalized, not requiring supplemental oxygen - requiring ongoing medical care (COVID-19 related or otherwise); 6. Hospitalized, not requiring supplemental oxygen - no longer requires ongoing medical care; 7. Not hospitalized, limitation on activities and/or requiring home oxygen; 8. Not hospitalized, no limitations on activities.2) Duration of hospitalization3) Death within 29 days of randomization4) ICU transfer within 29 days of randomization5) ECOG performance status at day 15 and 29 of randomization6) Incidence of grade III-V adverse events or SAEs (as defined by CTCAE version 5)7) Documented secondary bacterial or viral infection within 29 days of randomization.8) Mean frequencies of Th1 and Th17 T cells in blood mononuclear cells at 1, 2 and 4 weeks9) Mean levels of inflammatory serum biomarkers at 1, 2 and 4 weeks10) Gene expression profiles of T cells at 1, 2 and 4 weeks

OBJECTIVES	ENDPOINTS
11) Median titers of IgG antibodies to SARS-CoV-2 at 4 weeks 12) Survival at day 50-60 after randomization	

3. Background

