9.1 Inclusion Criteria

1. Hospitalized in participating facility.
2. Documentation of pneumonia with radiographic evidence of infiltrates by imaging (e.g., chest x-ray or CT scan).
3. Laboratory-confirmed SARS-CoV-2 infection as determined by PCR or other authorized or approved assay in any specimen collected within 72 hours prior to enrollment. Note – An exception must be requested to the Sponsor if ≥72 hours since positive test.
4. Symptoms suggestive of severe systemic illness with COVID-19, such as respiratory rate ≥ 30 breaths per minute, heart rate >125 beats per minute, oxygen saturation (O₂ sat) in the blood of <93% on room air at sea level or PaO₂/FiO₂ < 300 (see Appendix A).
5. 18 years of age or older
6. Patients with hematological parameters at screening consistent with ≤ grade 2 NCI CTCAE v5.0 toxicity: hemoglobin ≥8 g/dL, platelet count ≥50,000 K/mcl, an absolute neutrophil count (ANC) ≥1,000/mm³, and an absolute lymphocyte count (ALC) ≥500/mm³.

Protocol Title: Duvelisib Ameliorates Manifestations of Pneumonia in Established Novel Coronavirus Infection (DAMPEN-CI)

7. Patients with laboratory measurements of liver function at screening consistent with \leq grade 2 NCI CTCAE v5.0 toxicity: alanine aminotransferase (ALT) \leq 5X ULN; aspartate aminotransferase (AST) \leq 5X ULN; and bilirubin \leq 3X ULN.

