9.2 Exclusion criteria

Protocol Title: Duvelisib Ameliorates Manifestations of Pneumonia in Established Novel Coronavirus Infection (DAMPEN-CI)

1. Patients requiring mechanical ventilation (e.g. intubation, high-flow O₂ Bi-PAP or AIRVO) at the time randomization.
2. Patients receiving any investigational drugs other than drugs or therapies to treat COVID-19, with the exception of investigational immune-modulatory drugs as per section 5.4.
3. Pregnant women are excluded from this study because duvelisib is agent with the potential for teratogenic or abortifacient effects. Because there is an unknown but potential risk for adverse events in nursing infants secondary to treatment of the mother with duvelisib, breastfeeding should be discontinued before starting study drug and breastfeeding should not be resumed until at least 1 month after last dose of study drug.
4. Clinical suspicion that the etiology of acute illness (acute decompensation) is primarily due to a condition other than COVID-19
5. Known contraindication to duvelisib
6. Patients with hepatic cirrhosis as defined by symptomatic liver dysfunction; liver fibrosis by biopsy; ALT > 5X ULN, AST > 5X ULN, or bilirubin > 3XULN.
7. Patients with autoimmune diseases or patients on chronic immunosuppressive medications at the time of hospital admission or screening.
8. Active Hepatitis B or C infection, as determined by FDA-approved serology testing.

10. Number of Participants

We will be recruiting a total of 80 participants at Emory Healthcare and potential secondary sites, combined. We are expecting to have to consent 100 number of participants to reach our recruitment goal of 80. Patients will be registered after signing of the informed consent document and meeting all entry requirements.

11. Recruitment Methods

Investigators, nurses, and/or data managers review lists of patients who have COVID-19 and will determine if there are patients who might be eligible for a clinical trial. The nurse/data manager reviews accessible medical records to screen further for eligibility. Subjects will be identified by their treating physicians. Clinical care team at Winship will inform potential subjects about the known benefits and potential risks of a clinical trial as well as other available treatment options. Some of the subjects recruited for this protocol will be patients being treated at Emory and under the care of one or more of the study investigators.

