opportunity to stop the trial early due to futility or safety concerns. The only groups that will have access to unblinded interim data: (a) an independent data monitoring committee (IDMC); and (b) an independent statistical team whose role will be to generate the reports to be reviewed by the IDMC. The responsibility of any data-informed recommendations regarding continuing/stopping the study or modifying the study design/protocol be restricted to the IDMC.

Power Calculation

The reported incidence of death or mechanical intubation for patients with severe COVID-19 is approximately 40% (1). Local experience with COVID-19 patients at the Emory hospitals is consistent with this estimate, as 29% of all SARS-CoV-2 positive patients (n=800) are admitted to the ICU with COVID-19, and that 22% of all admitted patients are intubated, and 37% of intubated patients die in hospital. A favorable and clinically significant result from treatment with duvelisib in high-risk COVID-19 patients would be to reduce the composite incidence of death/mechanical ventilation from 40% to 15%. A sample size of 40 subjects for each treatment group will have >80% power to detect a 25% absolute reduction in the proportion of subjects who experience death or mechanical ventilation, comparing a predicted proportion of 40% death or intubation in the control arm to 15% death or intubation in the experimental arm receiving duvelisib treatment. The calculation is based on 10% type 1 error rate and two-sided Mantel-Haenszel test with one planned interim analysis when approximately 50% of sample enrolled (N=20/treatment). For

Analysis of Primary Endpoints

Analysis of the primary end-point will be based upon an intent-to-treat analysis of all subjects who are randomized to receive duvelisib/placebo. The primary endpoint is the proportion of patients who will require mechanical ventilation or experiencing death within 4-weeks (29 days) after randomization, which will be estimated with the corresponding 95% Clopper-Pearson confidence interval for the two arms separately. Fisher's Exact test will be used to test the difference between the two arms. In addition, a logistic regression will be used to estimate the odd ratio between the two arms controlling for the baseline covariates for an improved precision of the estimation (30).

Analysis of Secondary Endpoints

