Evaluable subjects will be all subjects who were randomized to receive duvelisib or placebo. The definition of secondary endpoints are listed in section 2. The descriptive statistics will mainly be applied to all secondary endpoints by treatment arms separately, such as frequency and percentage for categorical endpoints and mean, median, and standard deviation for numerical endpoints. They will be compared between treatment arms by Fisher's Exact test for categorical endpoints and Wilcoxon Rank-Sum test for numerical endpoints. For biomarkers measured repeated over time, generalized estimating equation (GEE) model will be used to test the difference in change pattern over time by two treatment groups using a nonlinear model. P-value will be adjusted for multiple comparison if necessary. Time to recovery is as the days from randomization to reach the desired NIAID ordinal scale ≥ 5 , a log-rank test will be used to compare the difference between the two arms. Survival rate at day 50 - 60 will be estimated by Kaplan-Meier method with log-rank test.

Interim Analysis for futility

The responsibility of any data-informed recommendations regarding continuing/stopping the study or modifying the study design/protocol be restricted to the independent data monitoring committee (IDMC), which is a part of the Winship data safety monitoring committee (DSMC). Upon 20 enrolled for each arm, an interim analysis will be carried out by two-sided Mantel-Haenszel test. O'Brien-Fleming boundary for futility is 2.373 on the Z score (equivalently: 0.991 on the fixed sample p-value scale). The trial may be terminated due to futility, or

Protocol Title: Duvelisib Ameliorates Manifestations of Pneumonia in Established Novel Coronavirus Infection (DAMPEN-CI)

following review by the IDMC of clinical and laboratory immune-monitoring data. Otherwise, the trial will continue enrolling patients until all 80 patients enrolled.

Stopping Rule for Safety

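### The ICU-transfer endpoint scores a death without an ICU stay as a good outcome and keeps patients already in an ICU in the denominator

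*Combined protocol and SAP*

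**What the plan says.** The endpoint appears in the synopsis (Section 1.1) and in Section 2 as "ICU transfer within 29 days of randomization", with nothing added. Section 15.1, Analysis of Secondary Endpoints, gives no fuller definition: "The definition of secondary endpoints are listed in section 2". The same paragraph fixes the analysis set, "Evaluable subjects will be all subjects who were randomized to receive duvelisib or placebo", and the test, "Fisher's Exact test for categorical endpoints and Wilcoxon Rank-Sum test for numerical endpoints". Under the missing-data rule in Section 15.1, secondary endpoints are analysed on observed cases without imputation. It does not mention death.

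On who may enter, Section 9.1 requires "Hospitalized in participating facility", with no limit to ward or ICU. Section 9.2 excludes "Patients requiring mechanical ventilation (e.g. intubation, high-flow O₂ Bi-PAP or AIRVO) at the time randomization". Being in an ICU is not itself an exclusion, and Sections 5.1 and 5.3 call the patients starting treatment critically ill. Randomisation is stratified by site only (Sections 1.2 and 11). ICU location is not among the baseline characteristics listed in Section 15.1.

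**The concern.** The endpoint is there to show whether duvelisib reduces clinical deterioration. Two groups of patients do not fit the definition.

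- **Death without an ICU stay.** The patient has the worst outcome but never has the event, so the analysis places that patient with those who recovered on the ward. More such deaths in one arm make that arm look better on this endpoint. A drug that prevented such deaths would get no credit for it.
- **Already in an ICU at randomisation.** Unless the patient leaves and returns, no new transfer can occur. The patient adds to the denominator and says nothing about the treatment effect on transfer.

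At stake is the reading of one secondary comparison, which could point the opposite way from mortality with no planned way to reconcile the two.

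**Working it through.** **Is there a plan figure to reproduce?** The plan states no rate, effect size or power for ICU transfer. As a check on the design inputs only, a chi-square calculation for the primary endpoint (40 per arm, 40% vs 15%, two-sided 10%) gives 81.5% power, in line with the stated figure of more than 80%.

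**Step 1. Apply the definition to each course.**

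| Course after randomisation | In denominator | Event |
|---|---|---|
| Ward, then home | yes | no |
| Ward, then ICU by day 29 | yes | yes |
| Ward, then death without ICU | yes | no |
| In ICU at randomisation, any outcome without leaving it | yes | no, on the natural reading |

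Rows one and three score the same.

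**Step 2. Deaths without ICU.** With 40 per arm, one such death lowers the arm's ICU rate by 1/40 = 2.5 points relative to counting it as an event. In general:

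ICU-only rate = ICU-or-death rate − rate of death without ICU.

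Assume 40% ICU-or-death in both arms (16 of 40), so there is no treatment effect on that outcome. Assume death without ICU is 5% on placebo and 10% or 15% on duvelisib. The documents give none of these rates.

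- Placebo: 40 − 5 = 35% (16 − 2 = 14 of 40)
- Duvelisib at 10%: 40 − 10 = 30% (16 − 4 = 12 of 40), an apparent benefit of 5 points
- Duvelisib at 15%: 40 − 15 = 25% (16 − 6 = 10 of 40), an apparent benefit of 10 points

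Counting ICU-or-death gives a difference of 0 in both cases. The illustration concerns the estimate, not its significance.

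**Step 3. Patients in an ICU at randomisation.** Let q be their share, and let pC and pT be the transfer rates among patients at risk.

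- Scored as non-events: (1 − q)pC − (1 − q)pT = (1 − q)(pC − pT)
- Scored as events: [q + (1 − q)pC] − [q + (1 − q)pT] = (1 − q)(pC − pT)

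The coding changes the level of the rates, but the difference shrinks by the same factor either way.

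For a size, take pC = 50% (the upper figure in Section 3.1) and pT = 25% (assumed), with the two-sided 10% level borrowed from the primary power calculation. Power is exact for Fisher's test. The first two power columns use 40 per arm. The last removes these patients, with the number left per arm in brackets.

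| q | Difference, (1 − q) × 25 | Power, non-events | Power, events | Power, removed (n) |
|---|---|---|---|---|
| 0 | 25.0 | 66.6% | 66.6% | 66.6% (40) |
| 5% | 23.75 | 63.4% | 60.5% | 66.9% (38) |
| 10% | 22.5 | 60.3% | 55.2% | 65.1% (36) |
| 20% | 20.0 | 53.8% | 45.8% | 57.3% (32) |
| 30% | 17.5 | 46.8% | 37.1% | 51.9% (28) |

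Removal keeps the difference at 25 points. Against non-event scoring it recovers 65.1 − 60.3 = 4.8 points of power at q = 10% and 57.3 − 53.8 = 3.5 points at q = 20%. With a lower control rate of 29%, halved by treatment (assumed), power at q = 10% is 34.0% with these patients as non-events and 33.8% with them removed, so nothing is gained.

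**The case against.** The strongest reply is that deaths are not hidden. Death within 29 days is the neighbouring secondary endpoint, death is part of the primary composite, it is the lowest category of the NIAID scale, and survival at day 50 to 60 is analysed. The ICU endpoint is one unpowered item in a list treated mainly descriptively, and no interim, safety or primary decision uses it. A composite of ICU transfer or death would overlap the primary composite. A one-line scoring rule with a table of ICU transfers and deaths by arm would be a lighter repair.

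Most of this stands and limits the weight of the point. It does not remove it. The separate death endpoint also counts deaths in the ICU, so it does not show which deaths were scored as non-events. Nor does it alter the Fisher comparison of ICU transfer. A scoring rule that still counted death without ICU as a non-event would leave that comparison as it is.

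A reader might also try to size the problem from the plan's own figures. The documents do not support this.

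- Section 15.1 reports that "29% of all SARS-CoV-2 positive patients (n=800) are admitted to the ICU with COVID-19, and that 22% of all admitted patients are intubated". Taking (29 − 22)/(100 − 22) = 7/78, about 9%, as the share in an ICU at entry fails because the two percentages have different stated denominators. Even with one denominator, the result would be patients ever in an ICU without intubation. That includes later transfers, which are true events, and high-flow patients, whom Section 9.2 excludes.
- Subtracting one third ventilated (Section 3.3) from about 40% ventilated or dead (Section 15.1) gives 40 − 33.3 = 6.7%, about 7%. This rests on rounded figures, and dying unventilated is not the same as dying outside an ICU.
- Adding the two, to about 16%, combines shares with different denominators and possible overlap.

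A reader might further infer that the direction of the bias in the difference depends on how sites code patients already in an ICU. Step 3 shows that it does not under uniform coding. Only the rate level moves in opposite directions.

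**Conclusion.** The concern holds in a limited form. Followed as written, the plan treats death without an ICU stay as equal to recovery and keeps patients not at risk in the comparison.

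- The first effect is worth 2.5 points per death, in favour of the arm where it occurs. The apparent benefit of 5 to 10 points rests on assumed rates and shows what is possible, not what is expected.
- The second effect is a shrinkage by (1 − q). The comparison is diluted only to the extent that such patients enrol. The documents do not give q, and the exclusion of ventilated and high-flow patients should keep it small.

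The documents do not support saying that the trial's main conclusion is at risk or that redefinition would recover much power. The primary endpoint is unaffected, and the power gain from removing patients already in an ICU is small or nil. The benefit is mainly that a lower ICU rate could be read as less deterioration. That is worth a short amendment before unblinding.

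**What to change.** In Sections 1.1, 2 and 15.1, define the endpoint as new ICU transfer or death within 29 days of randomisation, among patients not in an ICU at randomisation. Beside it, report by arm the number with a new ICU transfer and the number who died without one. Record ICU location at randomisation on the baseline case report form. In Section 15.1, state that this one comparison departs from the all-randomised set.

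The cost is wording in three places and one baseline item, since deaths are already collected. There are two downsides: the few patients in an ICU at entry leave this secondary comparison, and the new composite overlaps the primary endpoint. The component counts keep the ICU information visible.
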